I have read the protocol and agree to conduct the study as described herein.

PPD

[figure not shown]
STUDY IDENTIFICATION

Sponsor	Aqilion [name] Sweden
Sponsor's Study Contact	PPD  n
Medical Monitor	PPD 
Study Site	Labcorp Clinical Research Unit Ltd. United Kingdom
Principal Investigator	PPD 
Clinical Laboratory	Labcorp Clinical Pathology Services [name] United Kingdom
Bioanalytical Laboratory	Labcorp Early Development Laboratories Ltd. [name] United Kingdom
Statistician	PPD 

SYNOPSIS**Study Title**

A Randomized, Double-blind, Placebo-controlled, Single and Multiple Ascending Dose, and Food Effect Evaluation Trial to Evaluate the Safety, Tolerability, and Pharmacokinetics of AQ280 in Healthy Subjects

Objectives and Endpoints

Objectives	Endpoints
Primary:	

to evaluate the safety and tolerability of single and multiple ascending oral doses of AQ280, and to determine a safe therapeutic range of AQ280 in healthy subjects	
number of TEAEs per subjectclinically significant abnormalities in vital signs (systolic and diastolic blood pressure, pulse rate, and oral body temperature)abnormal ECG (QTcF interval of >450 msec for males and >470 msec for females, or change from baseline of >30 msec) measured from Day 1 (postdose) up until 48 hours postdose in Part A and up to the follow-up visit in Part Bclinically significant changes in laboratory evaluations
Secondary:	

to determine the PK of AQ280 after single and multiple oral dosesto determine the PK of the AQ280 main metabolite, AQ282, after single and multiple oral dosesto determine the effect of food on the PK of AQ280 after single oral dose	
Part A (SAD):
 
primary PK parameters derived from plasma concentration-time profile of AQ280: $AUC_{0-\infty}$, C_{max} ($AUC_{0-t_{last}}$ may be included as a primary PK parameter if $AUC_{0-\infty}$ cannot be calculated)primary PK parameters derived from plasma concentration-time profile of the AQ280 main metabolite, AQ282: $AUC_{0-\infty}$, C_{max} ($AUC_{0-t_{last}}$ may be included as a primary PK parameter if $AUC_{0-\infty}$ cannot be calculated)comparison of the primary PK parameters of AQ280 after single dose administration in the fasted state and in the fed state 
Part B (MAD):
 
primary PK parameters derived from plasma concentration-time profile of AQ280 on Day 1 and Day 7: AR, AUC_t, C_{max}primary PK parameters derived from plasma concentration-time profile of the AQ280 main metabolite, AQ282, on Day 1 and Day 7: AUC_t, C_{max}
Exploratory:	

Abbreviations: AR = accumulation ratio; AUC_{0-∞} = area under the concentration-time curve from time 0 extrapolated to infinity; AUC_{0-t_{last}} = area under the concentration-time curve from time 0 to the time of the last quantifiable concentration; AUC_T = area under the concentration-time curve over a dosing interval; CL/F = apparent total clearance; C_{max} = maximum observed concentration; CCI = electrocardiogram; CCI =

MAD = multiple ascending dose;
 PD = pharmacodynamic; PK = pharmacokinetic(s); QTcF = QT interval corrected for heart rate using Fridericia's method;
 SAD = single ascending dose; $t_{1/2}$ = apparent terminal elimination half-life; TEAE = treatment-emergent adverse event;
 t_{max} = time of the maximum observed concentration; V_z/F = apparent volume of distribution.

Study Design

This will be a Phase 1, randomized, double-blind, placebo-controlled, single and multiple ascending dose trial to evaluate the safety, tolerability, and pharmacokinetics (PK) of AQ280 conducted at a single clinical site. An investigation of food effect will be included in the single dose administration part of the study.

The decision to proceed to the next dose group or trial part will be taken by the dose escalation committee (DEC). Dose increases between groups may be up to 5-fold for dose levels where the next dose is predicted not to surpass exposure limits of 35 ng/mL (maximum observed concentration [C_{max}]) or 303 ng/mL *h (area under the concentration-time curve [AUC]), ie, exposures corresponding to the predicted minimally pharmacologically active dose of 10 mg; but will not be more than 3-fold at any subsequent dose increment.

Part A: Single ascending dose (SAD)

Five sequential dose groups with single administration of AQ280 capsule are planned, with 1 group including a second treatment period with dose administration under fed condition to investigate food interaction. Sentinel dosing will be used in the first dose group.

The single ascending dose (SAD) portion will include:

- A screening visit from 2 days up to 5 weeks before the dose of investigational medicinal product (IMP).
- An in-clinic treatment period of 4 days which includes a 48-hour period after the dose. Eligible subjects will be randomized on Day 1 to AQ280 or placebo prior to administration.
- A safety follow-up phone call will be conducted 1 week (± 2 days) after dose administration.

Dose administration will occur on Day 1.

Safety assessments will include adverse event (AE) reporting, vital signs, electrocardiograms (ECGs), clinical laboratory tests, and physical examination.

Blood samples to determine the PK of AQ280 and its main metabolite, AQ282, will be collected from predose up to 48 hours postdose.

Part B: Multiple ascending dose

Three sequential dose groups are planned, with subjects dosed once daily (QD).

The multiple ascending dose (MAD) portion will include:

- A screening visit from 2 days up to 5 weeks before the first dose of IMP.
- An in-clinic treatment period of 9 days which includes a 48-hour period after the last dose. Eligible subjects will be randomized on Day 1 to AQ280 or placebo prior to administration.
- A safety follow-up visit will be conducted 1 week (± 3 days) after the final dose.

For all subjects, dosing is planned to be QD on Days 1 to 7, inclusive, at approximately the same time each morning. The total daily dose administered will not exceed an exposure shown to be safe and well tolerated in Part A.

Safety assessments will include AE reporting, vital signs, ECGs, clinical laboratory tests, and physical examination.

Blood samples to determine the PK of AQ280 and its main metabolite, AQ282, will be collected from predose up to 24 hours postdose on Day 1; predose on Days 3 through 6; and from predose up to 48 hours postdose on Day 7.

Number of Subjects

Each group will have 8 subjects, randomized 6:2 to AQ280:placebo.

For Part A, the total will be approximately 40 subjects (8 subjects \times 5 groups).

For Part B, the total will be approximately 24 subjects (8 subjects \times 3 groups).

Additional groups may be utilized based on the need for more evaluations or groups may be removed based on data obtained.

Diagnosis and Main Criteria for Inclusion

The trial subject population are healthy subjects, male or female, 18 to 65 years, inclusive. Each group should contain both male and female subjects, preferably at least 2 subjects of each gender.

Furthermore, subjects with history of any significant infectious disease are excluded to mitigate the potential risk of infection. Light smoking during the trial is permitted, as this is not expected to interfere with AQ280.

Investigational Medicinal Products, Dose, and Mode of Administration

AQ280 capsule:

- Active substance: AQ280
- Dose form: capsule, hard
- Strength: 3 to 100 mg (dosage strength expressed as the free base moiety of AQ280)
- Start dose: 3 mg
- Method of administration: oral.

Reference Product and Mode of Administration

Placebo capsule:

- Active substance: none
- Dose form: capsule, hard
- Strength/dose: not applicable
- Method of administration: oral.

Duration of Subject Participation in the Study

Part A: up to approximately 6 weeks, including screening and safety follow-up. For the food effect evaluation group, up to approximately 8 weeks, including screening and safety follow-up.

Part B: up to approximately 7 weeks, including screening and safety follow-up.

Statistical Methods

Safety

Adverse events will be summarized for all treated subjects (safety analysis set) and will be presented by Medical Dictionary for Regulatory Activities preferred term and primary system organ class, and by group and treatment as the number of AEs and the number (percentage) of subjects with AEs. The percentage of subjects with AEs will be compared between treatments by a chi-square test or Fisher's exact test.

Vital signs, ECG, and laboratory parameters will be summarized by descriptive statistics (actual values and changes from baseline) at each assessment timepoint by group and treatment and by shift tables (according to normal ranges).

Pharmacokinetics

Plasma concentrations and PK parameters of AQ280 and its main metabolite, AQ282, will be listed and summarized by descriptive statistics per dose group and (for Part B only) day. Concentration-time profiles will be generated per dose group.

In Part A, where data are available, AQ280 dose proportionality will be examined across groups. The PK parameters AUC from time 0 extrapolated to infinity ($AUC_{0-\infty}$), AUC from time 0 to the time of the last quantifiable concentration ($AUC_{0-t_{last}}$), and C_{max} , will be analyzed for dose proportionality using a power model approach or analysis of variance (ANOVA) model as appropriate. Where data are available, the effect of food at 1 dose level in Part A will be investigated using ANOVA.

In Part B, the PK parameters AUC over a dosing interval (AUC_t) and C_{max} , on Day 7 will be analyzed for dose proportionality using a power model approach or ANOVA model as appropriate.

TABLE OF CONTENTS

TITLE PAGE	1
SPONSOR APPROVAL	2
INVESTIGATOR AGREEMENT.....	3
STUDY IDENTIFICATION	4
SYNOPSIS.....	5
TABLE OF CONTENTS.....	9
LIST OF TABLES AND FIGURES.....	11
LIST OF ABBREVIATIONS.....	12
1. INTRODUCTION	13
1.1. Overview.....	13
1.2. Summary of Nonclinical Pharmacology	13
1.3. Summary of Safety Pharmacology	13
1.4. Summary of Toxicology	13
1.5. Summary of Nonclinical Pharmacokinetics.....	14
1.6. Summary of Clinical Experience	15
1.7. Study Rationale.....	15
1.8. Benefit-risk Assessment.....	16
2. OBJECTIVES AND ENDPOINTS	16
3. INVESTIGATIONAL PLAN.....	18
3.1. Overall Study Design and Plan	18
3.1.1. Part A (Single Ascending Dose).....	19
3.1.2. Part B (Multiple Ascending Dose).....	21
3.2. Study Start and End of Study Definitions.....	22
3.3. Additional Groups.....	22
3.4. Discussion of Study Design, Including the Choice of Control Groups	22
3.4.1. Dose Interval.....	23
3.5. Selection of Doses in the Study	24
3.5.1. Starting Dose for Single Ascending Dose	24
3.5.2. Starting and Maximum Dose for Multiple Ascending Dose	24
3.6. Dose Escalation.....	24
3.7. Dose Escalation Stopping Criteria.....	25
4. SELECTION OF STUDY POPULATION	26
4.1. Inclusion Criteria	26
4.2. Exclusion Criteria	26
4.3. Subject Number and Identification	28

AUC _{0-t_{last}}	area under the concentration-time curve from time 0 to the time of the last quantifiable concentration
AUC _τ	area under the concentration-time curve over a dosing interval
CFR	Code of Federal Regulations
C _{max}	maximum observed concentration
CRO	contract research organization
CYP	cytochrome P450
DEC	dose escalation committee
EC	ethics committee
ECG	electrocardiogram
eCRF	electronic case report form
EDC	electronic data capture
EoE	eosinophilic esophagitis
FSH	follicle-stimulating hormone
GCP	Good Clinical Practice
HED	human equivalent dose
ICF	informed consent form
ICH	International Conference on Harmonisation
IL	interleukin
IMP	investigational medicinal product
JAK	Janus kinase
MAD	multiple ascending dose
NOAEL	no observed adverse effect level
PD	pharmacodynamic(s)
PK	pharmacokinetic(s)
QD	once daily
QTcF	QT interval corrected for heart rate using Fridericia's method
SAD	single ascending dose
SAE	serious adverse event
TMF	trial master file
ULN	upper limit of normal

1. INTRODUCTION

1.1. Overview

AQ280 is a highly selective inhibitor of Janus kinase (JAK) 1 that is being developed primarily for oral treatment of eosinophilic esophagitis (EoE). AQ280 blocks the signalling pathways of several cytokines including the interleukins (ILs) IL-4, IL-9, IL-13, IL-15 as well as thymic stromal lymphopoietin, which are considered key cytokines in the pathogenesis of EoE and many other immune-related diseases.

1.2. Summary of Nonclinical Pharmacology

AQ280 has been shown to inhibit JAK1 activity in a range of in vitro and in vivo assays, demonstrating its potency in inhibiting phosphorylation of tyrosine kinase substrates and activation of signal transducer and activator of transcription molecules. CCI [REDACTED]

[REDACTED]

[REDACTED]

[REDACTED]

[REDACTED]

1.3. Summary of Safety Pharmacology

CCI

[figure not shown]
[REDACTED]

1.4. Summary of Toxicology

CCI

[figure not shown]
[figure not shown]
[REDACTED]

CCI

1.5. Summary of Nonclinical Pharmacokinetics

CCI

CCI

[REDACTED]

Table 1: No Observed Adverse Effect Level Across Studies in Mice and Dogs

Study duration	Dose (mg/kg/day)	HED (mg)	C _{max} (ng/mL)	AUC (ng/mL*h)	Dose limiting findings
----------------	------------------	----------	--------------------------	---------------	------------------------

Mice

CCI

[REDACTED]

Dog

CCI

[REDACTED]

Abbreviations: AUC = area under the concentration-time curve; C_{max} = maximum observed concentration; F = female; HED = human equivalent dose; M = male; NOAEL = no observed adverse effect level.

O

C

1.6. Summary of Clinical Experience

AQ280 has not yet been tested in humans.

1.7. Study Rationale

This is the first time AQ280 will be administered to humans. The principal aim of this study is to obtain safety and tolerability data when AQ280 is administered orally as single and multiple doses to healthy subjects. This information, together with the pharmacokinetic (PK) data, will help establish the doses and dosing regimen suitable for future studies in patients. The effect of AQ280 on selected biomarkers will also be investigated. The study will also investigate the effects of food on the PK of AQ280 prior to patient studies.

1.8. Benefit-risk Assessment

Healthy subjects in the current study will not receive any health benefit (beyond that of an assessment of their medical status) from participating in the study. The risks of participation are primarily those associated with adverse reactions to the study treatment, although there may also be some discomfort from collection of blood samples and other study procedures. More information about the known and expected benefits, risks, and reasonably anticipated adverse events (AEs) associated with AQ280 may be found in the investigator's brochure.¹

2. OBJECTIVES AND ENDPOINTS

The objectives and endpoints of the study are presented in [Table 2](#).

Table 2: Objectives and Endpoints

Objectives	Endpoints
Primary: 
to evaluate the safety and tolerability of single and multiple ascending oral doses of AQ280, and to determine a safe therapeutic range of AQ280 in healthy subjects	
number of TEAEs per subjectclinically significant abnormalities in vital signs (systolic and diastolic blood pressure, pulse rate, and oral body temperature)abnormal ECG (QTcF interval of >450 msec for males and >470 msec for females, or change from baseline of >30 msec) measured from Day 1 (postdose) up until 48 hours postdose in Part A and up to the follow-up visit in Part Bclinically significant changes in laboratory evaluations
Secondary: 
to determine the PK of AQ280 after single and multiple oral dosesto determine the PK of the AQ280 main metabolite, AQ282, after single and multiple oral dosesto determine the effect of food on the PK of AQ280 after single oral dose	
Part A (SAD):
 
primary PK parameters derived from plasma concentration-time profile of AQ280: $AUC_{0-\infty}$, C_{max} ($AUC_{0-tlast}$ may be included as a primary PK parameter if $AUC_{0-\infty}$ cannot be calculated)primary PK parameters derived from plasma concentration-time profile of the AQ280 main metabolite, AQ282: $AUC_{0-\infty}$, C_{max} ($AUC_{0-tlast}$ may be included as a primary PK parameter if $AUC_{0-\infty}$ cannot be calculated)comparison of the primary PK parameters of AQ280 after single dose administration in the fasted state and in the fed state 
Part B (MAD):
 
primary PK parameters derived from plasma concentration-time profile of AQ280 on Day 1 and Day 7: AR, AUC_{τ}, C_{max}primary PK parameters derived from plasma concentration-time profile of the AQ280 main metabolite, AQ282, on Day 1 and Day 7: AUC_{τ}, C_{max}

Abbreviations: AR = accumulation ratio; AUC_{0-∞} = area under the concentration-time curve from time 0 extrapolated to infinity; AUC_{0-t_{last}} = area under the concentration-time curve from time 0 to the time of the last quantifiable concentration; AUC_T = area under the concentration-time curve over a dosing interval; CL/F = apparent total clearance; C_{max} = maximum observed concentration; CCI = electrocardiogram; CCI =

MAD = multiple ascending dose;
 PD = pharmacodynamic; PK = pharmacokinetic(s); QTcF = QT interval corrected for heart rate using Fridericia's method;
 SAD = single ascending dose; $t_{1/2}$ = apparent terminal elimination half-life; TEAE = treatment-emergent adverse event;
 t_{max} = time of the maximum observed concentration; V_z/F = apparent volume of distribution.

[figure not shown]
3. INVESTIGATIONAL PLAN

3.1. Overall Study Design and Plan

[figure not shown]
This will be a Phase 1, randomized, double-blind, placebo-controlled, single and multiple ascending dose trial to evaluate the safety, tolerability, and PK of AQ280. An investigation of food effect will be included in the single dose administration part of the study. The study will be conducted in 2 parts – Part A, single ascending dose (SAD) evaluations, including food effect, and Part B, multiple ascending dose (MAD) evaluations. Schematics of the planned groups for each part are presented in [Figure 1](#).

Figure 1: Planned Groups (Parts A and B)

Part A

Part B

Abbreviations: N = number of subjects; TBD = to be determined.

3.1.1. Part A (Single Ascending Dose)

Part A will comprise a single-dose, sequential group, escalating-dose design conducted in healthy adult male and female subjects; also incorporating a single-group, 2-period crossover arm investigating the effect of dosing AQ280 with food compared to dosing in the fasting condition. The first dose level administered is planned to be 3 mg AQ280.

A total of approximately 40 subjects are planned to be studied in 5 groups (Groups A1 to A5; with one of the groups including the food effect evaluation). In each group, 6 subjects will receive AQ280 and 2 subjects will receive placebo. The dose will be administered in the fasted state in accordance with the randomization schedule on the morning of Day 1 for all groups, including Period 1 for the food effect evaluation group (see [Section 3.1.1.1](#) for additional food-evaluation group requirements). Each group should contain both male and female subjects, preferably at least 2 subjects of each gender. Additional groups may be added based on the need for more evaluations or groups removed based on data obtained.

The first group in Part A will be divided into 2 cohorts, with each cohort being dosed at least 24 hours apart. The first cohort will comprise 2 subjects, with 1 subject receiving AQ280 and 1 subject receiving placebo. The second cohort will comprise 6 subjects, with 5 subjects receiving AQ280 and 1 subject receiving placebo. The 2 sentinel subjects (first cohort) will be dosed at least 24 hours before the second cohort of 6 subjects. Dosing of subjects in the second cohort will not occur if any of the dose escalation stopping criteria ([Section 3.7](#)) are met by the 2 sentinel subjects. Circumstances under which sentinel dosing may be introduced in other groups are detailed in [Section 3.4.1](#).

There will be a minimum of 9 days between dose escalations for each group.

Potential subjects will be screened to assess their eligibility to enter the study from 2 days up to 5 weeks before the dose of AQ280 or placebo. Each subject will participate in 1 group only and will reside at the study site from Day -1 (the day before dosing) to Day 3 of the treatment period, with dose administration occurring on Day 1. A safety follow-up phone call will be conducted 1 week (± 2 days) after dosing.

Each eligible subject will participate in 1 treatment period only, except for the food effect group, where each subject will participate in 2 treatment periods.

[figure not shown]
Based on the ongoing review of the safety, tolerability, and PK results, additional outpatient visits may be required.

Safety assessments will include AE reporting, vital signs, electrocardiograms (ECGs), clinical laboratory tests, and physical examination.

Blood samples to determine the PK of AQ280 and its main metabolite, AQ282, will be collected from predose up to 48 hours postdose.

An overview of the study design for Part A is shown in [Figure 2](#).

Figure 2: Study Schematic (Part A)

[figure not shown]
Abbreviation: PK = pharmacokinetics.

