3.4.1. Dose Interval

Following thorough review of all available nonclinical data (pharmacological and toxicological), dosing for the starting dose level in Part A (Group A) will be such that 2 subjects (1 AQ280 and 1 placebo) will be dosed at least 24 hours before the remaining 6 subjects.

At least 3 JAK inhibitors are approved for clinical use and several others are in Phase 3 clinical development. Thus, the risk of on-target suspected unexpected serious adverse reactions will be negligible. To minimize the consequence of any potential unknown off-target toxicity, sentinel dosing will be implemented for the first SAD group in Part A. Based on knowledge of the pharmacodynamic (PD) effects of other JAK inhibitors, in particular the JAK1-selective inhibitor abrocitinib, no effects are expected from a single dose beyond 24 hours after dosing. Therefore, a 24-hour interval between dosing of the sentinel subjects and the remaining subjects in the first group is considered sufficient, after review of available safety data.

Because of the well described target pharmacology and safety of other JAK inhibitors, sentinel dosing is not considered necessary for Part B, in which the predicted exposure will not exceed an exposure already shown to be safe and well tolerated in Part A.

Sentinel dosing may be introduced in other groups than in the first SAD group under the following circumstances:

- In case of any emerging clinical signs or AEs that do not meet stopping criteria but in the opinion of the DEC warrant a more cautious dose escalation.
- In case of non-linear PK that warrants a more cautious dose escalation.
- If the exposure is expected to exceed the NOAEL exposure in dogs, in which case further dose escalation will require a substantial protocol amendment.

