3.6. Dose Escalation

Doses will be administered in an escalating manner following satisfactory review by the sponsor and investigator of the safety and tolerability data (up to 48 hours postdose) and plasma PK data (up to 48 hours postdose) from the lower dose levels. Doses may be reduced and may be lower than the starting dose. There will be a minimum of 9 days between dose escalations to allow sufficient time for an adequate safety review.

Dose escalation in both Parts A and B will only occur if data from a minimum of 6 subjects have been reviewed from the previous lower dose group, such that data from a minimum of 4 subjects who have received AQ280 will be used to make the dose escalation decision.

The justification for this is as follows:

- The study treatment is of a known pharmacological class for which the on-target effects in humans are well characterized. Based upon nonclinical data, no clinically important off-target effects are expected within the proposed dose range.
- A minimum of 4 subjects receiving the active drug is considered sufficient to characterize the safety profile and PK/PD response to AQ280.

Prior to each dose escalation, the DEC, composed of the investigator, medical monitor, and sponsor medical representative as voting members and supported by additional team members (eg, pharmacokineticist) will review all available data in a blinded manner to ensure it is safe to proceed with the next planned dose level. An interim safety report, summarizing results from all available safety assessments, will be provided to the DEC prior to the dose escalation meeting. Any clinically significant results will be discussed by the DEC before dose escalation continues. Available interim PK data will also be reviewed to confirm that the study design remains appropriate. In the event of a disagreement between DEC voting members on the dose escalation decision, the decision of the investigator will be upheld.

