3.7. Dose Escalation Stopping Criteria

The study will be halted if 1 or more subjects experience a serious adverse event (SAE) that is considered to be related to investigational medicinal product (IMP) or 2 or more subjects in the same group experience severe AEs that are considered to be related to IMP. If, following an internal safety review, the sponsor deems it appropriate to restart the study, this can be done following approval of a substantial protocol amendment. Dosing of subjects, including any ongoing multiple dose groups, will be stopped immediately if any of the dose escalation stopping criteria are met.

In Parts A and B, following consultation with the sponsor and DEC, dose escalation will stop if:

- Clinically significant abnormal signs or symptoms of similar nature occur in 2 or more subjects in a group that, in the opinion of the investigator, warrant stopping of dose escalation.
- There is evidence of clinically significant increases in liver function tests defined as $3 \times$ upper limit of normal (ULN) for aspartate aminotransferase (AST), alanine aminotransferase (ALT), alkaline phosphatase, or gamma-glutamyl transferase or $2 \times$ ULN for total bilirubin in 2 or more subjects in a group (confirmed with repeat testing).
- Clinically significant increases in serum creatinine, defined as $1.5 \times$ ULN (confirmed with repeat testing), in 2 or more subjects in a group.
- Hemoglobin decrease of >3.5 g/dL compared to Day -1 levels (confirmed by repeat testing) in 2 or more subjects in a group.

- Neutrophil count $<1.5 \times 10^9/L$ and/or a platelet count $<100 \times 10^9/L$ (confirmed with repeat testing) in 2 or more subjects in a group.
- Clinically significant increases in activated partial thromboplastin time or prothrombin time, defined as $2 \times \text{ULN}$ (confirmed by repeat testing) in 2 or more subjects in a group.
- The systemic exposure of AQ280 is predicted to exceed a C_{max} of [REDACTED] ng/mL (based on [REDACTED] mg/kg/day dose in males and females in 4-week dog study) and/or an AUC of [REDACTED] ng/mL*h (based on 5 mg/kg/day dose in males in 16-week dog study) in any individual subject; ie, systemic exposure will be no greater than the exposure at NOAEL in the most sensitive species.

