- QT interval corrected for heart rate using Fridericia's method (QTcF) increases >60 ms compared to baseline (predose for Part A or Day 1 predose for Part B) and/or absolute QTcF values >500 ms (confirmed with repeat testing) in 1 or more subjects in a group.

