5.3. Randomization

The randomization code will be produced by the statistics department at Labcorp Drug Development using a computer-generated pseudo-random permutation procedure.

In Parts A and B, 2 subjects in each group will be randomly assigned to receive placebo.

For the first group in Part A (Group A1), sentinel dosing will occur whereby 2 subjects (1 active and 1 placebo) will be dosed on 1 day and, providing no safety concerns arise, the remaining 6 subjects will be dosed at least 24 hours later.

Subjects in the food effect evaluation group in Part A will receive the same treatment in Treatment Periods 1 and 2.

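### The hard stop before Group A1's second cohort uses full-group criteria: 7 of 10 need two affected subjects, so the single AQ280 sentinel can trigger only 3

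*Protocol*

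**What the plan says.** Protocol 3.1.1 splits Group A1 into a sentinel pair and a second cohort of six, five of them on AQ280. Of the pair it says: "The first cohort will comprise 2 subjects, with 1 subject receiving AQ280 and 1 subject receiving placebo". Its rule for going on is: "Dosing of subjects in the second cohort will not occur if any of the dose escalation stopping criteria" of Section 3.7 are met by those two subjects.

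Section 3.7 opens with two conditions that halt the study and then lists eight that stop escalation. Most are worded for a group. The severe-event condition needs "2 or more subjects in the same group experience severe AEs that are considered to be related to IMP". The hemoglobin bullet, typical of the laboratory ones, requires a fall "compared to Day -1 levels (confirmed by repeat testing) in 2 or more subjects in a group". Only a few can be met by one person; the QTcF bullet, for example, ends "confirmed with repeat testing) in 1 or more subjects in a group".

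Two other places bear on the same decision. Section 5.3 says that, "providing no safety concerns arise, the remaining 6 subjects will be dosed at least 24 hours later". Section 3.4.1 finds a 24-hour gap sufficient provided the safety data in hand have been reviewed, and gives the purpose: "To minimize the consequence of any potential unknown off-target toxicity, sentinel dosing will be implemented for the first SAD group in Part A".

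**The concern.** The criteria were written for deciding whether to raise the dose after a group has been treated. For that decision Section 3.6 requires that "data from a minimum of 4 subjects who have received AQ280 will be used to make the dose escalation decision". The sentinel decision has one such subject.

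Unknown off-target toxicity can show itself only in the sentinel who received AQ280. A rule that needs a second affected subject therefore waits for the placebo recipient to show it too. If the AQ280 sentinel has one related severe but non-serious event, or one laboratory value past a Section 3.7 limit, the criteria-based rule does not fire. Whether five more people receive AQ280 is then decided by judgement, without a stated single-subject trigger.

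**Working it through.** The documents give no figure for this point, so there is none to reproduce. The check is a count.

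**Section 3.7 criteria, by the number of affected subjects each needs**

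| Criterion | Place in 3.7 | Subjects needed | AQ280 sentinel alone can meet it? |
|---|---|---|---|
| Related SAE | opening paragraph | 1 | yes |
| Related severe AEs | opening paragraph | 2 | no |
| Signs or symptoms of similar nature | bullet | 2 | no |
| Liver tests | bullet | 2 | no |
| Creatinine | bullet | 2 | no |
| Hemoglobin | bullet | 2 | no |
| Neutrophils or platelets | bullet | 2 | no |
| aPTT or PT | bullet | 2 | no |
| Predicted exposure | bullet | 1 | yes |
| QTcF | bullet | 1 | yes |

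Needing two: 1 + 6 = 7 of 10, or 6 of the 8 bullets. Needing one: 1 + 2 = 3 of 10. Five of the seven are laboratory criteria, each also requiring a repeat test.

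**What the two-subject requirement means here.** In a full group it is 2/8 = 25% of subjects. In the sentinel pair it is 2/2 = 100%.

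**Chance that a rule fires.** For a given event, let p1 be its probability in the AQ280 sentinel and p0 in the placebo sentinel, taken as independent.

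- Two-subject rule: p1 × p0.
- Either-subject rule: 1 − (1 − p1)(1 − p0).

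The rates below are illustrative assumptions; the documents give none.

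| p1 | p0 | Two-subject rule | Either-subject rule |
|---|---|---|---|
| 1.0 | 0 | 0 | 1.00 |
| 1.0 | 0.05 | 0.05 | 1.00 |
| 0.3 | 0.05 | 0.015 | 1 − 0.7 × 0.95 = 0.335 |

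The first row needs no assumption about drug risk. If the placebo sentinel is well, a two-subject criterion cannot be met, however certain the event is on AQ280.

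**Laboratory timing.** Appendix 3 allows four full laboratory evaluations in Part A (4 × 9.3 mL = 37.2 mL). The Part A schedule in Appendix 6 places them at screening, check-in, 24 hours and 48 hours. None falls after dosing and before 24 hours, which is the earliest time the second cohort may be dosed.

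A partly redacted row of the same schedule has samples at predose and at 1, 4, 8 and 12 hours. Its 24-hour point is covered by the hematology and chemistry panels. Appendix 3 agrees: 8 samples less 3 optional ones leaves 5 drawn separately. Some safety analytes may therefore be measured early; which ones, and how soon results return, cannot be read from the text.

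**The case against.** The strongest reply is that Section 3.1.1 is not the only gate. It says when the second cohort must not be dosed; it does not say that dosing goes ahead in every other case. Section 5.3 sets no minimum number of subjects, so one concern in one sentinel is enough, and a related severe event is a concern on any sensible reading. Section 3.4.1 separately requires a look at the safety data.

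Much can also be seen before 24 hours. Vital signs are taken at 1, 2, 4, 6, 8 and 12 hours and safety ECGs at 2, 4 and 8 hours, and telemetry runs over the first day. The 3 mg dose is below the predicted minimally active dose of 10 mg. Section 7.3.2 allows extra or earlier laboratory tests.

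All of this stands, and it rules out two stronger readings. A reader might infer that the second cohort would be dosed despite a serious problem in the AQ280 sentinel. The documents do not support that: a related SAE halts the study on its own, a confirmed QTcF breach is a single-subject trigger, and Sections 5.3 and 3.4.1 cover the rest by judgement. A reader might also infer that no postdose laboratory data exist before the second cohort is dosed. That does not follow either: the interval may be longer than 24 hours, and the redacted early samples may include safety analytes.

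The reply does not make the written rule workable. Sections 5.3 and 3.4.1 give no threshold, do not define a concern, and do not say which results must be in hand. Section 3.1.1 does not refer to Section 5.3. The committee review in Section 3.6 is tied to dose escalation, not to the step between the two cohorts. Nothing in Section 3.1.1 adapts the two-subject criteria to a pair.

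**Conclusion.** The point holds as a defect in one stated rule, not as an absence of protection. Seven of the ten criteria behind the Section 3.1.1 hard stop cannot be met by the AQ280 sentinel alone, so for those the hold rests on judgement. The step affects six subjects in one group, five of them on AQ280.

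The count rests on reading the two-subject wording literally for the two sentinels, which is what Section 3.1.1 asks for. It needs no event rate. The laboratory part is narrower: it applies only when the second cohort is dosed before the 24-hour results are back, and only to the full panels.

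Severity is minor to moderate. An event at 3 mg is not expected, but sentinel dosing exists for the unexpected, this is the first human exposure, and the remedy is cheap. No endpoint or analysis changes.

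**What to change.** Replace the gate sentence in Protocol 3.1.1 with a single-subject hold that can be released after review:

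> Dosing of the second cohort will be held if either sentinel subject individually has a related SAE, a related severe AE, a clinically significant sign or symptom of concern to the investigator, or a laboratory, QTcF or exposure value beyond a Section 3.7 threshold (including a value awaiting repeat testing), or if any other safety concern arises (Section 5.3). Dosing may proceed only after documented review, with unblinding under Section 5.4 where that section permits it, concludes that it is safe, unless a Section 3.7 study-halt or stopping criterion has itself been met. The sentinels' 24-hour safety laboratory results will be reviewed before the second cohort is dosed.

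The rule says either sentinel because site staff do not normally know which one received AQ280. It is a hold, not a bar, so that a chance finding in the placebo sentinel does not end the group. Signs and symptoms get their own clause because a criterion about similar findings in several subjects has no single-subject form.

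The cost is a wording amendment. No subjects, visits or tests are added: the 24-hour sample is already scheduled, and the interval is already stated as a minimum. The downside is a possible short delay from a chance event in either sentinel or from laboratory turnaround, which the documents do not state. SAP 3.1.1 repeats the gate only as description, so no SAP analysis changes.
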